Enhancing inhibitory control via non-invasive neurostimulation may improve the efficacy and efficiency of ERP for OCD. The right inferior frontal gyrus (rIFG) is a particularly promising target for such an approach. This region is a key node in neurocircuitry underlying inhibition of a prepotent response. The location of rIFG makes it easily accessible to tDCS, a type of non-invasive neurostimulation delivering a weak electrical current (1-2 mA) via two electrodes placed on the scalp. Neurostimulation via tDCS modulates neuronal excitability by changing membrane potentials and can enhance behavioral plasticity. In healthy individuals, tDCS over rIFG improves inhibitory control of a prepotent response during the SST, a well-established response inhibition paradigm. Such effects have been seen after a single tDCS session, and when stimulation over rIFG was delivered during a course of inhibition training sessions over four days. We propose to extend this approach by coupling tDCS and behavioral training, i.e., ERP, to inhibit compulsive behaviors in OCD.

C. Experimental Method

1. Brief Description of Subjects

For the TIES (Therapy Integrating Exposure and Stimulation) study we will recruit 32 patients with a primary diagnosis of OCD, aged 18-65, with clinically significant OCD symptoms (Y-BOCS total score of ≥ 16). Participants will be naïve to tDCS and will never have completed a minimally adequate trial of ERP (see human subjects section below for additional inclusion/exclusion criteria).

2. Study Design

For this study we will recruit 32 patients with a primary diagnosis of OCD. Each participant will undergo an assessment which will include a structured clinical interview, brief assessments of depression, anxiety, OCD symptoms, and medication and treatment history. Participants will be randomized to one of two combination interventions: Exposure and response prevention (ERP) plus active transcranial direct current stimulation (tDCS) over right inferior frontal gyrus (rIFG) or ERP plus sham tDCS over rIFG. Each group will complete 1 session of psychoeducation and treatment planning, followed by 10 90-minute sessions of their assigned combination intervention. Participants will also complete a post-treatment and one month follow-up assessment.

3. Specific Procedures or Treatments

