To monitor for symptom change, short assessments will be given at baseline, and approximate weekly (see Table 1) during treatment (for clinical symptoms monitoring), post-treatment, and 1-month after treatment, using the Y-BOCS^{43, 44}; BDI-II⁴⁵ (see "Screening," above); and the Beck Anxiety Inventory (BAI),⁴⁶ to assess general anxiety symptoms. The

Patient Ex/RP Adherence Scale (PEAS)⁴⁷ will be used at each ERP session to assess adherence to ERP homework, since adherence relates to treatment outcome.⁴⁸ Patients will also complete the 8-item Client Satisfaction Questionnaire (CSQ-8)⁴⁹ at post-treatment and 1-month follow-up to assess satisfaction with the intervention. A modified version of the Systematic Assessment for Treatment Emergent Events-Specific Inquiry (SAFTEE-SI) will be administered assess for emergent side-effects. This is a self-report measure which inquires about the presence and severity of 55 of the most commonly reported side effects in clinical trials, as well as how much reported side effects bother patients or interfere with daily activities. The SAFTEE-SI will be administered at baseline, at sessions 1, 3, 5, 7, and 9, at post-treatment, and at 1 month follow-up. At each administration, the evaluator or therapist will note items rated more bothersome than during the previous administration. The therapist or evaluator will inquire further about each such item, including asking for a description of the side effect, when it occurs, how much it interfered, and what the participant attributes the symptom to. The therapist or evaluator will also inquire in an open-ended fashion about any other adverse effects experienced which are not listed on the SAFTEE-SI and will document the nature and tolerability of any additional side-effects reported. For any item rated "severe," or if the participant reports that side effects are interfering with daily activities "markedly," the therapist or evaluator will notify Dr. [Name] MD (PI) (or covering physician) immediately and Dr. [Name] (or covering physician) will provide further evaluation as medically necessary. Any item rated as "moderate" or

Date most recently revised (02/16/18)

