Behavioral Intervention: Exposure and Response Prevention (ERP) is a specific type of CBT that has been shown to be effective at reducing symptom severity in OCD. ERP involves individuals placing themselves in anxiety-provoking situations (exposure) and inhibiting their compulsions (response prevention). Compulsive behaviors usually serve as an attempt to reduce distress. By refraining from compulsions, participants gain corrective information that the feared situation is not dangerous. ERP typically proceeds in a graded manner, as it will here, beginning with exposure to more manageable situations and progressing to more difficult situations as treatment continues. The behavioral intervention here includes 11 sessions in total: one 90-minute session including psychoeducation and treatment planning followed by 10 ERP sessions lasting approximately 90-min each. These 11 sessions will be delivered twice-weekly over a 5.5 week period. All intervention sessions must be completed within a maximum of seven weeks. Between sessions, self-directed ERP will be assigned as homework. During each of the 10 ERP sessions, tDCS will be delivered for 20 min immediately prior to the ERP exercise. We selected a 10-session ERP intervention (plus 1 session of psychoeducation and treatment planning) in an attempt to balance feasibility with allowing sufficient sessions to evaluate treatment effects. While 10 sessions is shorter than most manualized ERP protocols, ERP interventions of similar length, session frequency, session content, and design have often been used to evaluate the efficacy of augmentation of ERP with pharmacotherapy including D-cycloserine (Kushner et al., 2007; Storch et al., 2010; Wilhelm et al., 2008). All sessions will be audio recorded using digital voice recorders in order to assess for treatment fidelity. As stated below, 15% of sessions will be reviewed to ensure adherence to the treatment protocol. In order to obtain an unbiased assessment of therapist fidelity to the intervention, participants will not be allowed to opt out of session recording. (Handling of digital audio recordings to protect against loss of confidentiality and privacy is outlined below under III. Human Subjects.)

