future research studies. (2) To minimize the risk of distress arising from the assessment procedure, study staff that has been adequately trained in the assessment battery will complete all assessments, and [the PIs] will supervise all assessors. (3) To minimize risks due to tDCS, all participants will be carefully screened prior to tDCS for contraindications to tDCS. Moreover, we will obtain a release to gather information from participants' current medical providers for screening purposes and ongoing clinical record keeping. All tDCS will be administered by a trained member of the research staff under the supervision of a credentialed physician (Dr. [Name] or covering physician). Use of an electrically isolated power source (i.e., battery-powered DC stimulation device) also protects against delivery of more intense currents than intended. Participants will be closely observed for signs of skin burns, discomfort, or other stress. Participants will be closely monitored to ensure the electrode sponges stay moist with saline in order to help prevent burns by improving electrode-to-skin contact. Participants will have the option of discontinuing the study at any time and will be explicitly instructed to inform the experimenters immediately if they experience any discomfort. The experimenter will inform the supervising physician about any participant who has significant skin discomfort or a skin lesion after current delivery. If there is any doubt about the mental or physical status of an individual after testing, the PI or other supervising physician will evaluate the participants and make a recommendation for follow-up care, if required. Telephone or in-person follow-up will be arranged as needed and will not be considered a protocol deviation. Adverse effects will be monitored regularly using the SAFTEE-SI. This measure includes symptoms of hypomania, including feeling hyper, unable to sit still, changes in appetite, and sleep disturbance, as well as a number of frequently reported side effects in clinical trials. Any participant judged on clinical grounds to have suffered adverse effects will thus be evaluated and treated as necessary and withdrawn from the study, if necessary. For each SAFTEE item, participants are asked to report how bothersome each symptom on the form has been for him/her in the past week, with response options "None," "Mild," "Moderate," or "Severe." Additionally, a single item inquires about how much all reported side-effects have bothered the participant or interfered with daily activities (response options: "No side effects," "Mildly," "Moderately," or "Markedly"). The SAFTEE-SI will be administered at baseline, once per week during the 5.5 week protocol, at post-treatment, and at 1 month follow-up. At each administration, the evaluator will note items rated more bothersome than during the previous administration and will inquire further about each such item. The therapist or evaluator will also inquire in an open-ended fashion about any other adverse effects experienced which are not listed on the SAFTEE-SI and will document the nature and tolerability of any additional side-effects reported. For any item rated "severe," or if the participant reports that side effects are interfering with daily activities "markedly," the therapist or evaluator will notify Dr. [Name] MD (PI) (or covering physician) immediately. Dr. [Name] (or covering physician) will provide further evaluation as medically necessary and we will take appropriate safety measures such as study withdrawal and/or referral to higher level of clinical care, if necessary. Any item rated as "moderate" or "moderately" interfering will be reported to Dr. [Name] by the therapist or evaluator within 24 hours. All other reported side-effects endorsed on the SAFTEE-SI will be discussed with Dr. [Name] during weekly meetings of study staff. Follow-up or further evaluation will occur as medically necessary. (4) To minimize the risk of distress due to treatment procedures, we have selected a treatment which has been shown to be efficacious in reducing OCD symptoms. While this treatment involves clients placing themselves in situations which provoke anxiety, this is necessary and effective for clinical improvement and generally represents no more distress than is experienced in daily living for these individuals. Participants will be informed that they will be encouraged to

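### The SAFTEE-SI looks back one week, but the only form after post-treatment comes at 1 month, so about three quarters of follow-up is not systematically covered for listed side effects

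*Combined protocol and SAP*

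**What the plan says.** The recall period is given in III.D.1 (Measures to minimize potential risks): "participants are asked to report how bothersome each symptom on the form has been for him/her in the past week". II.C.3 (Monitoring Assessments) gives the schedule: "The SAFTEE-SI will be administered at baseline, at sessions 1, 3, 5, 7, and 9, at post-treatment, and at 1 month follow-up". III.D.1 describes the same schedule as "once per week during the 5.5 week protocol, at post-treatment, and at 1 month follow-up".

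Session timing is in II.C.3 (Behavioral Intervention): "These 11 sessions will be delivered twice-weekly over a 5.5 week period", with an outer limit: "All intervention sessions must be completed within a maximum of seven weeks". For the period after treatment, II.C.2 (Study Design) says only: "Participants will also complete a post-treatment and one month follow-up assessment".

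III.D.1 also says what the form contains: "This measure includes symptoms of hypomania, including feeling hyper, unable to sit still, changes in appetite, and sleep disturbance". In both II.C.3 and III.D.1, the open-ended question that goes with each form is confined to "any other adverse effects experienced which are not listed on the SAFTEE-SI".

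**The concern.** A symptom form with a fixed look-back covers the whole study period only if the forms are no further apart than the look-back. Here the look-back is 7 days and the last interval is a month. A listed effect that begins after post-treatment and resolves more than a week before the 1-month visit falls within no item's recall. The two built-in supplements do not reach it. The open-ended question is worded for unlisted effects. The item-by-item inquiry is prompted by a rating worse than on the previous form, and an effect that came and went between windows produces no such rise. The escalation steps for moderate and severe ratings also need a rating to act on.

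What is at stake is how an uneventful follow-up can be read. III.D.1 names the SAFTEE-SI as the regular monitor of adverse effects, and the plan schedules a form at 1 month. If few listed effects appear on that form, the finding describes roughly the last quarter of the month, and a reader could easily take it to describe all of it.

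**Working it through.** **Inputs**
- Recall: 7 days (III.D.1).
- Forms: baseline, sessions 1, 3, 5, 7 and 9, post-treatment, 1 month (II.C.3, Monitoring Assessments).
- Pace: 11 sessions, two per week, with a seven-week (49-day) maximum (II.C.3, Behavioral Intervention).
- Follow-up: 1 month. No visit window is given, so I take 28 to 31 days as an assumption.
- Time from session 10 to post-treatment: not given, so I show alternatives.

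**The plan's own figure.** 11 sessions / 2 per week = 5.5 weeks, as stated. The spacing is 7 / 2 = 3.5 days, so odd-numbered sessions are 2 × 3.5 = 7 days apart.

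**Formula.** Uncovered days between two consecutive forms = max(0, interval − 7).

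**Follow-up**
- 28 days: 28 − 7 = 21 uncovered; 21/28 = 75%.
- 30 days: 30 − 7 = 23 uncovered; 23/30 = 77%.
- 31 days: 31 − 7 = 24 uncovered; 24/31 = 77%.

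**Treatment at the planned pace**
- Sessions 1 to 9: 7 − 7 = 0 uncovered in each of the four intervals.
- Session 9 to post-treatment: 3.5 days plus the lag after session 10. This stays within 7 days if the lag is at most 3.5 days. With a 7-day lag (assumption), 10.5 − 7 = 3.5 days are uncovered.

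**Treatment stretched evenly to 49 days.** The spacing depends on whether 49 days is divided into 11 or 10 gaps.
- 49/11 = 4.45 days; odd sessions 8.9 days apart; 1.9 uncovered per interval (21%). Over four intervals this is 7.6 days, or 19% of the 40.1 days from session 1 to session 10.
- 49/10 = 4.9 days; odd sessions 9.8 days apart; 2.8 uncovered per interval (29%). Over four intervals this is 11.2 days, or 25% of the 44.1 days from session 1 to session 10.

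In the stretched case, forms tied to odd sessions are also more than a week apart, so the schedule in II.C.3 no longer delivers the weekly administration described in III.D.1.

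Table 1, as it reads in the available text, marks the SAFTEE-SI at every session and at neither later visit. Its columns appear damaged, so I have not relied on it. Forms at every session would leave no treatment gap.

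**The case against.** The strongest reply is that this form is not the only route. Participants are told to raise discomfort with staff at once and to telephone or page about adverse events (III.D.1), and the PIs complete an Adverse Events Form (III.D.3). The training section (II.E) mentions debriefing and evaluation of adverse effects after stimulation. Reasons for withdrawal are documented (II.C.3, Participant Withdrawal), and a significant adverse reaction to tDCS is one of them. Ratings of moderate or severe are escalated whether or not they have risen.

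Most of this stands, and it rules out several stronger readings that a reader might infer:

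- **That listed effects go unrecorded.** The documents do not support this. Such effects are not systematically elicited, but they can be volunteered and recorded. What remains is that volunteering depends on the participant noticing the effect and thinking it worth a call, which is least dependable for mild effects.
- **That the plan leaves gaps during treatment.** At the planned pace it leaves none between session forms. Seven weeks is an outer limit, not the schedule.
- **That Aim 1 is undermined.** The Aim 1 hypothesis rests on retention, treatment completion and patient report. The revised analysis plan (II.C.4) names session completion and client satisfaction as the primary outcomes. No Aim 1 analysis names the SAFTEE-SI.
- **That hypomania is likely to be missed.** The reports described in III.C arose during a course of daily stimulation, and the documents identify no delayed-onset risk. The hypomania items share the follow-up gap with every other listed item, and no more than that.
- **That an effect which led a patient to stop is lost.** The documented reason for withdrawal gives it a place in the record, even if a later past-week form would not rate it.

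A last objection is that lengthening the recall of the ratings would disturb the comparison with the previous form that prompts further inquiry. That is right, and the remedy should leave the ratings alone.

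**Conclusion.** The point holds for follow-up. With a 7-day recall and no form between post-treatment and 1 month, 21 to 24 of 28 to 31 days (75% to 77%) are not systematically covered for listed side effects, and the open-ended question as worded does not make up for it. This rests on the stated recall and schedule, plus the assumption that 1 month means 28 to 31 days.

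For treatment it holds only conditionally: about 2 to 3 days per interval if sessions are spread evenly toward the seven-week limit, or a few days before post-treatment if that visit falls more than 3.5 days after session 10.

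The consequence is limited. A 1-month form with few listed effects would not by itself support a statement that none occurred in the month after treatment. Nothing in the documents shows bias between arms, since both have the same form and schedule.

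**What to change.** Keep the past-week rating for every item, so that each form stays comparable with the one before. In II.C.3 (Monitoring Assessments) and III.D.1, widen the open-ended inquiry at every administration after baseline: ask about any adverse effect, on the form or not, since the last completed form, and record onset and stop dates. Apply this also to the first form completed after early discontinuation. State the recall period in II.C.3 as well, since it now appears only in III.D.1. Reconcile the two descriptions of timing, so that it is clear whether forms follow odd-numbered sessions or the calendar week when sessions are delayed.

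The cost is a sentence in each section and on the interview form, with no added visit and no change to the escalation steps. Recall over a month is less exact than over a week, and the interview takes a little longer.

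The revised analysis plan refers to the final sample in the past tense. If the forms have already been collected, the report should say that the 1-month SAFTEE-SI ratings describe the preceding week only, and that other follow-up effects rest on spontaneous report.

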Assessment Training and Monitoring of Treatment Integrity. Assessments will be completed by a trained, supervised, advanced (i.e., BA or higher) evaluator who will be kept blind to participant’s group assignment. The evaluator will initially be trained to an inter-rater reliability of ≥ 0.80 . Assessments will be audio recorded and will be checked periodically to minimize rater drift. To Date most recently revised (02/16/18)

ensure fidelity to the intervention and consistency between therapists, study therapists will undergo training in this approach including directed readings and regular supervision of on-going cases. Treatment sessions will be audio recorded and a randomly selected 15% of sessions will be reviewed to ensure adherence to the treatment protocol.

Participant Withdrawal. Participants may be withdrawn from the study for any of the following reasons: 1) A significantly deteriorating clinical course, such as the emergence of active suicidal ideation or a need for hospitalization, 2) Significant adverse reaction to tDCS, assessed using a modified version of the Systematic Assessment for Treatment Emergent Events (SAFTEE), 3) Serious physical illness, 4) Missing two consecutive study visits, 5) Initiation or reinstitution of other treatment (psychosocial treatment with proven efficacy, psychotropic medication changes) during the acute treatment phase, 6) Investigators' decision that withdrawal from the study is in the participant's best interest, 7) Participant's decision to withdraw. Reasons for withdrawal will be documented, participants will be referred for appropriate treatment, and we will make every attempt to conduct scheduled follow-ups with those who withdraw. The current study will employ several measures to minimize attrition, including frequent contact with participants for the duration of the study and compensation for participants' time for post-treatment and follow-up assessment visits.

4. Data Analysis

Original Data Analysis Plan:

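### The blinded evaluator may question participants about worsened side effects, including their attributions, and nothing requires the Y-BOCS to be rated first

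*Combined protocol and SAP*

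**What the plan says.** Section II.C.3 (Assessment Training and Monitoring of Treatment Integrity) has assessments done by one kind of rater, described as "i.e., BA or higher) evaluator who will be kept blind to" the participant's group.

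The SAFTEE-SI side-effect form is described in two places.

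- Section II.C.3 (Monitoring Assessments): "At each administration, the evaluator or therapist will note items rated more bothersome than during the previous administration". On who then asks, it says: "The therapist or evaluator will inquire further about each such item, including asking for a description of the side effect". Besides the time of occurrence, this inquiry is to cover "how much it interfered, and what the participant attributes the symptom to". On the visits: "The SAFTEE-SI will be administered at baseline, at sessions 1, 3, 5, 7, and 9, at post-treatment, and at 1 month follow-up".
- Section III.D.1: "At each administration, the evaluator will note items rated more bothersome than during the previous administration and will inquire further about each such item". The sentence after that names both roles again: "The therapist or evaluator will also inquire in an open-ended fashion about any other adverse effects experienced". The steps for notifying the physician also name both roles.

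The Revised Data Analysis Plan (section II.C.4, Aim 2) makes the Y-BOCS the primary clinical outcome. It is to be read from group means and direction of effect at post-treatment and 1 month, without a test. Section II.C.3 also plans a questionnaire on the integrity of the blind at post-treatment and does not name who completes it.

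**The concern.** Asking a participant what a symptom is due to can draw out a belief about whether the stimulation was real. If the person asking then rates the Y-BOCS, the rating is made with that belief in mind, whether the belief is right or wrong. The revised plan relies on the direction of a difference in mean Y-BOCS in a small sample, so its reading depends on the ratings being made blind. The protocol commits to a blinded evaluator but leaves open a route by which that person may hear about presumed allocation before rating.

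**Working it through.** No statistical figure in the plan bears on this point. The check sets the sections side by side and counts visits.

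1. **Who asks.** Section II.C.3 names evaluator or therapist for noting worsened items and for following them up. Section III.D.1 names only the evaluator for these two tasks. The two sections agree on the open-ended question and on notification (both roles). The difference is therefore confined to one sentence, but both wordings permit the evaluator.

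2. **Is this the Y-BOCS rater?** The same word is used throughout, no second evaluator role is defined, and assessments are assigned to the blinded evaluator. That is the natural reading, but it is an inference.

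3. **Do the visits coincide?** SAFTEE-SI visits in the text of II.C.3: 1 baseline + 5 sessions (1, 3, 5, 7, 9) + 1 post-treatment + 1 at 1 month = 8. Section II.D lists the same 8 assessment visits. Section II.C.3 schedules the Y-BOCS at baseline, about weekly in treatment, at post-treatment and at 1 month. The overlap is 8 of 8, and 8 − 1 = 7 of these come after baseline. If session 1 assessments precede the first stimulation (not stated), 7 − 1 = 6 follow some stimulation. Both Aim 2 time points are among them. Table 1 as extracted marks visits differently for both instruments. That may be an extraction fault, so the count uses the text.

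4. **Is an order set?** No section sets one. Table 1 lists the Y-BOCS above the SAFTEE-SI, but it is a visit schedule and not an order of administration.

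5. **What might be heard?** The attribution question appears only in II.C.3. Follow-up is triggered only by items rated worse than last time; the open-ended question has no such trigger. In III.D.1, "participants are asked to report how bothersome each symptom on the form has been for him/her in the past week", so session 1 may carry little about stimulation, and the 1-month form covers a week after stimulation has ended.

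6. **How large is the effect?** The documents do not say how often the evaluator asks, how often an attribution concerns allocation, or how far hearing one moves a Y-BOCS score. No bias can be computed.

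**The case against.** The case against is substantial. Only one sentence drops the therapist, which may be shorthand. Section II.E trains the clinicians who give tDCS in evaluating adverse effects and in administering the modified SAFTEE, which suggests that therapists would do most of the asking at sessions. Participants are tDCS-naive, the ramped sham is described as effective, and common side effects are said to be similar under sham. Evaluators are trained to a reliability of at least 0.80. The order of instruments within a visit often sits in an operations manual. The revised plan speaks of the final sample as already known, so a new visit order may come too late.

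Much of this stands, and it keeps the point modest. It does not remove it. If the sentence in III.D.1 is shorthand, II.C.3 still lets the evaluator ask. Sham quality and similar side effects bear on whether symptoms reveal allocation; they do not stop the rater from hearing a belief. Reliability concerns agreement between raters, not an expectation they may share. The training in II.E makes the fix easy but does not reserve the task for therapists. The planned questionnaire may show a problem but cannot prevent one. Lateness shifts the weight to reporting.

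A reader might infer that the evaluator must collect attributions at 5 sessions before the post-treatment Y-BOCS and at 5 + 1 = 6 visits before the 1-month one. The documents do not support this. It joins the evaluator-only wording of III.D.1 to an attribution question found only in II.C.3, where the therapist may ask it instead.

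**Conclusion.** The point holds as an avoidable risk to the blind on the primary clinical outcome. The two sections differ on who follows up worsened items, both allow the evaluator, and nothing separates that inquiry from the Y-BOCS rating or puts it afterwards at the 8 shared visits. It rests on one inference, that the evaluator in the SAFTEE-SI text is the blinded rater of II.C.3. Confidence is medium; this is a worthwhile cheap improvement, not a fatal flaw.

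A reader might infer that the blind was broken or that the Y-BOCS ratings are biased. The documents show neither: an attribution is not the allocation and may not concern it, and any bias may be zero. Nor should a reader infer that reordering removes the exposure. An inquiry made after the post-treatment rating still precedes the 1-month rating. Side effects are also discussed at weekly staff meetings, and the documents do not say whether the evaluator attends. What would remain cannot be counted.

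**What to change.** **For participants still to be assessed.**

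- Reconcile II.C.3 and III.D.1 so that at treatment sessions the therapist makes both the follow-up of worsened items and the open-ended adverse-effect inquiry.
- At any visit where the evaluator must ask, complete and record the Y-BOCS first.
- Keep the evaluator out of the side-effect discussion at weekly staff meetings.
- Leave the form and the notification steps as they are.

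**For participants already finished**, probably the main part:

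- Report from existing records who made the inquiry and whether it came before the Y-BOCS, where this is known.
- Report the planned blind questionnaire by arm, descriptively and not as proof that the blind held.
- State the limitation beside the Y-BOCS means.

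**Cost.** The visit order and the reassignment need no extra staff, because II.E already covers therapist training. If forms do not show who asked, the audio recordings of assessments could be checked before the erasure at study end set in III.D.2. With a final sample below the planned 32, hence at most 31, that is at most 31 × 2 = 62 post-treatment and 1-month recordings. At an assumed 5 to 10 minutes each, this is 62 × 5 / 60 = 5.2 to 62 × 10 / 60 = 10.3 hours.

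**Downside.** More side-effect questions would be asked by therapists, whose blind status is not stated, and tolerability belongs to Aim 1. Record who asked at each visit and note it beside any tolerability comparison between arms.
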